Although the preliminary results of the new Thulium laser look promising, there are no clinical randomized trials comparing it to the Holmium laser, which is the current standard laser used for URS lithotripsy.

Aims of the study:

The primary aim of the study is to compare the stone free rate (SFR) following URS lithotripsy with Holmium and Thulium lasers. SFRs will be compared both for ureteral stones, renal stones and ureteral and renal stones in total.

Secondary aims are to compare the results of the two lasers in terms of operating times, intraoperative complications, postoperative complications and the rate of post endoscopic JJ-stenting.

Hypothesis:

1. The SFR, defined as no residual fragments detected on CT scan 3 months after the URS, is higher following lithotripsy with Thulium laser compared to Holmium laser. The corresponding H_0 is that "*there is no difference in SFR following laser lithotripsy with the two lasers.*"
2. Operating time following Thulium laser lithotripsy is shorter compared to Holmium laser. H_0 : "*There is no difference in the operating time between the two laser machines.*"
3. There are less intraoperative complications during Thulium laser lithotripsy compared to Holmium laser. H_0 : "*There is no difference in intraoperative complications between the two laser machines.*"
4. There are less postoperative complications (infections, readmissions, strictures) during Thulium laser lithotripsy compared to Holmium laser. H_0 : "*There is no difference in postoperative complications between the two laser machines.*"
5. Fewer patients will need post endoscopic insertion of JJ-stent following Thulium laser lithotripsy compared to following Holmium laser lithotripsy. The corresponding H_0 is that "*there is no difference in the frequency of post endoscopic JJ-stent placement following laser lithotripsy with the two lasers.*"

Study design:

The study is planned performed as a prospective randomized trial. All patients ≥ 18 years scheduled to URS lithotripsy at the day surgery unit at HUH are invited to be enrolled in the study. After written informed consent, patients are randomized to URS lithotripsy with either Holmium laser or Thulium laser.

Randomization:

The randomization is performed electronically with the same number of patients in each group. The results of the randomization are being kept in sealed and consecutively numbered envelopes that is opened just before starting the endoscopic procedures in each patient.

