Patients and data sampling:

All patients ≥ 18 years scheduled for URS lithotripsy at the day surgery unit at HUH are basically eligible for inclusion in this study. Patients with either ureteral stones, renal stones or both can be included. The number of patients/procedures needed to be included in the study is specified in the Power analysis-section below.

The following data need to be registered:

- *Preoperative status:* Age, sex, ASA-status, indication for surgery, earlier surgery for same stone, stone status, acute/planned surgery, prestenting-status, infection.
- *Peroperative characteristics:* Randomization status, primary surgeon, antibiotic prophylaxis, operating time, need for safety guide wire and access sheath, type of endoscope (semi-rigid/flexible), balloon dilatation, impacted stone, successful access to the stone, laser modality, laser settings, laser time and energy used, dusting or fragmentation, retrieval of fragments or left for spontaneous passage, surgeon's assessment of post

- endoscopic stone free status, complications, placement of JJ-stent.
- *Postoperative status:* Length of hospital stay, immediate complications that need urgent treatment, complications after discharge requiring readmission, 3-months follow-up with CT scan (SFR, stricture rate).

The data will be plotted in a registration form which will be available both electronically and on paper. If paper form is used, the data will be registered electronically subsequently and the paper-form maculated. Completed registration-forms are transferred to a SPSS database for statistical analyses.

The registration-forms and the database will be stored at Helse-Bergen's scientific and research server in a designated file assigned from the Data Protection Officer. An ID-Key file combining personal ID to the registration form will be stored at a designated server for this purpose at Helse-Bergen's research servers. Only the project manager ([name]) will have access to this ID-Key file.

The registration forms and the ID-Key file will be kept on the server for five years after the study has been completed in accordance with the law. After five years the data will be made anonymous in terms of deleting the ID-Key file.

Power analysis:

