In an earlier study, we found the 3-months SFR after Holmium laser URS lithotripsy to be 54.2% using a strict definition of *no* residual fragments detected on CT scan³. Although this is a strict definition, it leaves no room for personal judgement whether a patient is stone free or not. The definition is therefore suitable for this study purpose.

We expect the Thulium laser to be more efficient in clearing stones than the Holmium laser, with a total SFR of around 80% after URS lithotripsy using this laser.

Comparison of the SFRs between Holmium and Thulium laser will be done using the χ^2 -test. An effect size of 0.3 is considered appropriate assuming the SFRs after Holmium and Thulium laser lithotripsy to be 54.2% and 80%, respectively. The α error probability is set to 0.05 and the power (1- β error probability) is set to 0.8. Comparison of the SFRs following URS with the

two lasers with χ^2 -test is based on a 2 x 2 table, and in this case with only 1 degree of freedom (Df).

Using G*Power, version 3.1.9.4 for power analysis, the total sample size is calculated to be 88. To compensate for possible non-evaluable patients, a total of 120, i.e. 60 patients in each group, are planned to be included in the study.

Statistical analyses:

Statistical analyses will be performed using IBM SPSS Statistics 25 or higher (IBM, Armonk, NY). A p -value < 0.05 will determine statistical significance.

Continuous variables will be compared using independent-samples t -tests, or in the cases where a normal distribution is not met, Mann-Whitney U test. Exact chi-squared test and Fisher's Exact test are used comparing categorical variables.

Ethical considerations, ethical approval and patient consent

Holmium laser lithotripsy is the gold standard during URS today and is in use worldwide. Preliminary results with the new Thulium laser seem promising, however, no randomized trials comparing the outcome of the two laser modalities exists. The planned study therefore seems to be highly clinically relevant. In addition, the new Thulium laser is approved for use during endoscopic lithotripsy and the patients should therefore not be exposed to extra risk of harm using this laser.

Applications for approval by The National Committees for Research Ethics in Norway and The Data Protection Authorities at HUH will be sent prior to study start. In addition, the study will be registered in the clinical research database for randomized trials, ClinicalTrials.gov.

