All patients eligible for inclusion in the study will receive oral and written information. Participation in the study is voluntarily, and the patient can choose to withdraw at any point during the study process. Inclusion in the study will only be done after the consent form is signed. The patient information and consent form used for this purpose is obtained from The National Committees for Research Ethics in Norway's website (https://helseforskning.etikkom.no/frister/malforinformasjonsskriv?p_dim=34672).

Laser settings

The laser settings in the two study groups need to be standardized. The following laser settings are suggested as the start-up settings. In the cases of insufficient effect, higher energies can be applied but then need to be registered.

Ureteral stones: 0.4 J at 6 Hz (2.4 watts), long pulse

Renal stones: 0.4 - 0.8 J at 6 - 20 Hz (2.4 - 16 watts) for Holmium and
0.6 - 0.8 J at 30 Hz (18 - 24 watts) for Thulium.

The initial settings for the Thulium laser when treating renal stones are at a higher watt-level compared to the Holmium laser settings, and is therefore expected to be more efficient. However, the fact that the Thulium laser is able to deliver more energy needs to be considered when comparing the clinical outcome of the two lasers.

Study progress

The date for completing the data registration form, patient information and consent form, and application for approval by The National Committees for Research Ethics in Norway is set to 18th of August 2020.

During August 2020 the application form to The Data Protection Authorities at HUH will be sent. Prior to study start the study will also be registered in the clinical research database for randomized trials, ClinicalTrials.gov.

Inclusion of patients and ureteroscopies is expected to start in October 2020, and the inclusion is expected to close during March 2021.

Data analyses and writing a draft is set to spring 2021. Final manuscript ready for submission is planned during the summer 2021.

Funding

No external funding is planned. Hopefully, the project can be completed during regular working hours at Haukeland University Hospital and the University of Bergen.

Conflicts of interest

[name] is a consultant for Olympus, who was not involved in the design, collection, analyses, interpretation or reporting of the data. The two other authors have nothing to disclose.

Publication of data

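### The protocol conceals allocation until endoscopy but states no masking of patients or post-discharge staff afterwards, so the readmissions and infections in Hypothesis 4 could be biased in either direction

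*Combined protocol and SAP*

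**What the plan says.** The Study design section says: "The study is planned performed as a prospective randomized trial". It does not mention blinding. The Randomization section describes concealment by sealed, numbered envelopes, each "opened just before starting the endoscopic procedures in each patient", and the text on allocation stops there.

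Hypothesis 4 reads: "There are less postoperative complications (infections, readmissions, strictures) during Thulium laser lithotripsy compared to Holmium laser". Under Patients and data sampling, the postoperative data include immediate complications needing urgent treatment, "complications after discharge requiring readmission", and a 3-month CT follow-up for stone-free rate and strictures. The protocol gives no definition of infection, no admission criteria and no adjudication.

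The same section lists randomization status and laser modality among the data to be registered, and names one form for everything: "The data will be plotted in a registration form which will be available both electronically and on paper".

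The one argument about judgement is in the Power analysis section. It says of the strict CT definition that "it leaves no room for personal judgement whether a patient is stone free or not". That argument covers the stone-free rate only. The ethics section adds that "the patient can choose to withdraw at any point during the study process".

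**The concern.** Envelopes opened at surgery protect the assignment. They do nothing for outcomes that arise after the envelope is open. A readmission after day surgery passes through two human decisions: the patient asks for help, and a clinician admits. Whether an infection is noticed and recorded follows a similar route. If either person knows the laser and holds a view about it, the count in one arm can move without any true difference.

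Two things are at stake. The first is how a difference under Hypothesis 4 can be read, because an effect of the laser could not be separated from an effect of knowing the laser. The second is smaller: patients who know their arm might attend the 3-month CT, or withdraw, at different rates by arm, and that would reach the primary endpoint through missing data.

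The design makes patient masking plausible. Both arms have ureteroscopic laser lithotripsy in the same day surgery unit, and the arm is unknown until just before the procedure.

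**Working it through.** **What the plan fixes.** It plans 120 patients, 60 per arm (Power analysis). Categorical outcomes are compared by exact chi-squared or Fisher's exact test at p < 0.05 (Statistical analyses). The plan gives no complication rate and no power for Hypothesis 4, so there is no figure of its own to reproduce on this point. Its only sample-size figure, 88, does reproduce (chi-square, w = 0.3, 1 df, α 0.05, power 0.8), but it concerns the stone-free rate and is not affected here.

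**What has to be assumed.** The true risk p is the same in both arms and is taken over 3-20%. Knowledge of the arm multiplies the observed risk in one arm by k, with k = 1 (no bias), 1.25 or 1.5.

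**Formula.** With i events in the inflated arm and j in the other,

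P(false result favouring the other arm) = Σ over i > j of Bin(i; 60, kp) × Bin(j; 60, p) × 1[two-sided Fisher p-value for i/60 vs j/60 < 0.05].

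The spurious gap in risk is p(k − 1).

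| Base risk p | Gap at k = 1.25 / 1.5 (points) | k = 1 | k = 1.25 | k = 1.5 |
|---|---|---|---|---|
| 3% | 0.75 / 1.5 | 0.2% | 0.5% | 1.0% |
| 5% | 1.25 / 2.5 | 0.5% | 1.4% | 2.9% |
| 8% | 2 / 4 | 0.9% | 2.6% | 5.8% |
| 12% | 3 / 6 | 1.2% | 4.0% | 9.6% |
| 20% | 5 / 10 | 1.4% | 6.2% | 18.1% |

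With a milder inflation of 10% (k = 1.1), the chance is 0.8% at p = 5% and 2.7% at p = 20%.

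**Reading the table.** At p = 20% and k = 1.5, the expected counts are 60 × 0.30 = 18 against 60 × 0.20 = 12. At p = 5% and k = 1.5, they are 60 × 0.075 = 4.5 against 60 × 0.05 = 3. Fisher's test at this size needs splits such as 0 vs 6, 2 vs 10 or 4 vs 13 to reach significance. A few extra events therefore seldom produce a false positive when events are rare.

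**Direction.** The arms are equal in size and the test is symmetric. The same figures apply whichever laser has the inflated count, and nothing in the calculation chooses between them.

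**Primary endpoint.** No calculation is possible. It would need CT attendance by arm and the stone status of non-attenders, and the documents give neither.

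**The case against.** The strongest case against the point is that it rests on silence. What patients are told belongs in the patient information. That is a separate form on the ethics committee's template, due on 18 August 2020, after the protocol's date of 5 August 2020. Consent pages were removed from the text under review. A reader might infer that patients are told their laser, but no visible passage says so. What stands is narrower: the visible protocol states no masking after the envelope is opened.

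A reader might also infer that the bias would favour Thulium. The investigators' own expectation does lean that way. Patients' behaviour is another matter. The protocol describes Holmium as the worldwide standard and Thulium as a device with about 30 local procedures. Caution about a new device could raise Thulium readmissions just as readily, which would work against Hypothesis 4. The documents do not support a direction.

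The size is assumed throughout, and the 18% figure needs the highest value of both inputs. Infections are not quantified separately. Strictures are recorded at the 3-month CT follow-up and depend little on what patients or ward staff know, apart from attendance.

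Finally, the documents do not establish that masking would be nearly free. They do not describe the anaesthesia, who runs follow-up, or what readmitting staff can see. The surgeon must know the laser, and it stays in the operating record. Neutral wording in handover or discharge papers also changes clinical documentation. For these reasons staff masking is the weaker part of the remedy and patient masking the stronger.

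**Conclusion.** The point holds as an omission that exposes a secondary hypothesis to avoidable bias in an unknown direction. Bias is neither demonstrated nor shown to favour one laser. Its importance depends on how common the events are. If true risks are near 3-5%, it hardly matters for significance testing. If they approach 20% and knowledge of the arm changes the count by half, it could mislead. Both the base risks and the inflation factors are assumptions. Any effect on the CT-based primary endpoint would act only through attendance and is likely small. This is a low-priority improvement that does not threaten the trial's main conclusion.

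**What to change.** In Randomization, add: *The patient is not told which laser was used until the 3-month CT is completed, unless disclosure is clinically needed.* Put a matching line in the patient information. Where feasible, use neutral wording such as *study laser* in routine handover, and keep the actual laser in the operating record. In the report, state who was and was not masked.

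This needs no extra staff, procedure, sample size or change of analysis. The cost is some discipline in communication and, if handover wording is changed, a small change to clinical documentation. Masking will be incomplete, because the surgeon and anyone who reads the operating record will know the arm.

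### Hypothesis 4 compares postoperative infections, but the data list does not provide for infections treated after discharge without readmission, so the infection rate would be under-counted for its label.

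*Combined protocol and SAP*

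**What the plan says.** Under Aims of the study, the secondary aims cover "operating times, intraoperative complications, postoperative complications and the rate of post endoscopic JJ-stenting". Hypothesis 4 spells out the third of these: "There are less postoperative complications (infections, readmissions, strictures) during Thulium laser lithotripsy compared to Holmium laser". Infections and readmissions are named there as two different things.

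The section Patients and data sampling lists what has to be registered. The postoperative items are length of stay, then "immediate complications that need urgent treatment, complications after discharge requiring readmission", then "3-months follow-up with CT scan (SFR, stricture rate" at the follow-up visit. Infection is named as a data item once, in the preoperative group: "acute/planned surgery, prestenting-status, infection".

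The population is "All patients ≥ 18 years scheduled for URS lithotripsy at the day surgery unit at HUH".

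Under Statistical analyses, categorical variables are compared with exact chi-squared and Fisher's exact tests at p < 0.05. The Power analysis section plans 60 patients per group. Its calculation concerns the stone-free rate only; no infection rate and no power for Hypothesis 4 are given.

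**The concern.** An outcome named in a hypothesis should have a data item that measures it. Here the item is narrower than the name. An infection that appears at home and is treated without readmission fits nothing on the postoperative list, and in day surgery much of the period at risk falls after discharge. Any post-discharge infection that is recorded is, by the wording of the list, also a readmission, so two components that the hypothesis separates partly become one.

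Two things are at stake. The infection rate in each arm would be reported under a label broader than what was counted. And a non-significant result could be presented as no difference in infections when the less severe ones were not collected. The protocol states that no randomized comparison of these lasers exists, so its complication rates may be relied on.

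**Working it through.** **Step 1. Match each component of Hypothesis 4 to the data list.**

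| Component | Postoperative item that records it | Coverage |
|---|---|---|
| Readmissions | Complications after discharge requiring readmission | Yes, for complications |
| Strictures | Stricture rate at the 3-month CT follow-up | Yes |
| Infections, immediate and needing urgent treatment | Immediate complications | Yes |
| Infections after discharge, readmitted | Complications requiring readmission | Yes, but counted as readmissions too |
| Infections after discharge, not readmitted | None | Not provided for |

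The 3-month follow-up is described as yielding stone-free status and stricture rate. The documents give no definition of infection, no time window, and no source such as a patient question or a record check.

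**Step 2. The plan's own figure.** The only computed figure is the total of 88 for the primary endpoint. With effect size w = 0.3, 1 degree of freedom and alpha 0.05, the noncentrality is N × w² = 88 × 0.09 = 7.92, which gives power 0.804. So 88 reproduces. It says nothing about Hypothesis 4, and the point here does not depend on it.

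**Step 3. Illustrate the loss of events.** The documents give neither an infection rate nor the share treated without readmission, so both are assumed and varied:

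- n = 60 per arm (Power analysis), taking every patient as evaluable;
- true infection rates p1 (Holmium) and p2 (Thulium): 15% vs 5%, 10% vs 5%, 20% vs 10%;
- captured share q, the same in both arms: 1, 1/2, 1/3;
- two-sided Fisher's exact test at 0.05, as named in Statistical analyses.

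Expected recorded infections are 60 × p × q. For 15% vs 5% at q = 1/2 that is 60 × 0.15 × 0.5 = 4.5 vs 60 × 0.05 × 0.5 = 1.5.

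Power = Σ over a, b from 0 to 60 of Bin(a; 60, p1·q) × Bin(b; 60, p2·q) × 1[Fisher p(a, b) < 0.05].

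| True rates | q = 1: events, power | q = 1/2: events, power | q = 1/3: events, power |
|---|---|---|---|
| 15% vs 5% | 9 vs 3, 33% | 4.5 vs 1.5, 9% | 3 vs 1, 3% |
| 10% vs 5% | 6 vs 3, 9% | 3 vs 1.5, 2% | 2 vs 1, 1% |
| 20% vs 10% | 12 vs 6, 25% | 6 vs 3, 9% | 4 vs 2, 4% |

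The choice of test matters. For 15% vs 5%, an uncorrected chi-squared test would give 46%, 22% and 14%, but that is not the test the plan names for categorical variables.

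**Step 4. What does not change.** If q is the same in both arms, the ratio of the recorded rates still equals p1/p2, for example 7.5% / 2.5% = 15% / 5% = 3. The absolute rates and their difference shrink by the factor q: at q = 1/2 a difference of 10 percentage points is recorded as 5.

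**The case against.** The data list is a summary. The registration form itself is not among the documents, and under Study progress it was due for completion on 18 August 2020, after the protocol date of 5 August 2020. It may hold more than the list. This stands: a reader might infer that infections outside hospital are never captured, but the documents support only that the list does not provide for them.

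A reader might also infer that the infection outcome cannot be analysed. It can. Infections needing urgent treatment or readmission are recorded under the same rule in both arms, and that is a usable, fairly objective outcome. The mismatch is one of scope and label. Nor do infections merge wholly into readmissions, because immediate urgent complications are a separate item.

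A third tempting reading is that the gap favours one laser. Nothing in the documents shows that under-capture differs by arm.

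The power illustration rests entirely on assumed rates. Even with full capture, power is 33% at best in the cases shown, so incomplete capture is not the main reason why a null result would be uninformative. That is correct, but it leaves the under-counted rate itself untouched.

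Finally, wider capture by patient recall is softer than a readmission count, and the documents describe no blinding of patients. This is a real cost, and a reason to report the two levels of severity separately. It does not justify leaving the label and the data item in disagreement.

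**Conclusion.** The point holds as a mismatch between a named secondary outcome and its data source. If the list is followed as written, infections treated after discharge without readmission are left out, the infection rate is too low for its label, and its post-discharge part duplicates readmissions. Strictures and readmissions do have a source, and serious infections are recorded.

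The size is unknown, because it depends on the share of infections treated without readmission. Under the assumed rates, losing half the events takes Fisher power from 9–33% down to 2–9%, and losing two thirds takes it to 1–4%. These figures assume 60 evaluable patients per arm and equal capture in both arms. Whatever the capture, this trial could not establish that infections do not differ. The issue is modest in weight: one component of a secondary hypothesis, with no effect on the primary stone-free comparison.

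**What to change.** Before the registration form is finalised, add one field to the Postoperative status list, completed at the 3-month follow-up already planned: any postoperative infection treated since the procedure. State a definition and a time window, record the date and whether treatment was in or outside hospital, and use the same wording in both arms.

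Report as separate descriptive secondary lines: all infections; infections needing urgent treatment or readmission; readmissions; strictures. Give counts and confidence intervals by arm, so that no extra significance claims are created.

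The cost is one or two form fields at an existing contact. The downside is some patient-recalled data, possibly from patients who know their laser; this should be stated as a limitation, with the hospital-treated subset shown beside it.

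If the field is not added, restate Hypothesis 4 as infections needing urgent treatment or readmission, and say in the analysis plan that a null result will not be read as no difference in infections overall. That costs one sentence in each place.

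### The sample size of 88 uses w = 0.3, but the stated stone-free rates give w = 0.275: power at 88 is about 73%, and 105 evaluable patients are needed

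*Combined protocol and SAP*

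**What the plan says.** All the figures are in the combined protocol and SAP. The Power analysis section takes a Holmium rate of 54.2% from an earlier study by the same group and expects Thulium to do better, "with a total SFR of around 80% after URS lithotripsy using this laser". It then sets the effect size: "An effect size of 0.3 is considered appropriate assuming the SFRs after Holmium and Thulium laser lithotripsy to be 54.2% and 80%, respectively". The test is a chi-square test on a 2 x 2 table with 1 degree of freedom, at alpha 0.05 and power 0.8. From G*Power, "the total sample size is calculated to be 88". Enrolment is set higher: "To compensate for possible non-evaluable patients, a total of 120, i.e. 60 patients in each group, are planned". No expected loss rate is given. The Randomization section specifies equal group sizes.

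The Power analysis section names the chi-square test for the stone-free rate. The Statistical analyses section then says, without excepting the primary endpoint: "Exact chi-squared test and Fisher's Exact test are used comparing categorical variables".

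**The concern.** For a 2 x 2 table with equal arms, w is not a free choice once the two rates are given; it follows from them. The value 0.3 is therefore either a separate assumption or a rounding, and the text presents it as belonging to 54.2% and 80%. The required sample size is proportional to 1/w², so a modest upward rounding of w lowers the sample size noticeably and in the favourable direction.

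This is the only sample size justification in the plan, and it concerns the primary aim. Anyone relying on it would take 88 evaluable patients as enough for 80% power and would read the other 32 of the 120 as spare. The endpoint requires a CT scan three months after surgery and patients may withdraw at any time, so some loss is to be expected. A final evaluable number in the nineties would look adequate against the written target and would not be.

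**Working it through.** **Inputs.** From Power analysis: p1 = 0.542 (Holmium), p2 = 0.80 (Thulium), alpha = 0.05, target power 0.80, chi-square test with 1 df, w = 0.3, N = 88, enrolment 120. From Randomization: 1:1 allocation. Sidedness is not stated in words; a 1-df chi-square test is non-directional, so alpha is treated as two-sided.

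**Step 1: reproduce the plan's figure.** Power is the probability that a noncentral chi-square variable (1 df, noncentrality N·w²) exceeds the 95% point of the central distribution. With w = 0.3:

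- N = 87: power 79.9%
- N = 88: noncentrality 88 × 0.09 = 7.92, power 80.4%

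The smallest N reaching 80% is 88, as stated. Both the method and the source of the figure are therefore clear.

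**Step 2: w from the stated rates.** With equal arms, w = |p1 − p2| / (2·√(p̄(1 − p̄))), where p̄ = (0.542 + 0.80)/2 = 0.671.

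w = 0.258 / (2 × √(0.671 × 0.329)) = 0.258 / 0.9397 = 0.2746.

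In reverse, w = 0.3 with a 54.2% Holmium rate requires a Thulium rate of about 82.1%.

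**Step 3: same method, w = 0.2746 (w² = 0.07538).**

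| Evaluable N | N·w² | Power |
|---|---|---|
| 88 | 6.63 | 73.1% |
| 104 | 7.84 | 79.95% |
| 105 | 7.92 | 80.3% |
| 106 (53 per arm) | 7.99 | 80.7% |
| 120 | 9.05 | 85.3% |

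**Step 4: does another formula rescue 88?** Totals for 80% power computed directly from 54.2% and 80%:

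- Two-sided: 102 (pooled variance), 102 (arcsine), 98 (unpooled variance), 118 (continuity-corrected)
- One-sided: 80 (pooled variance), 96 (continuity-corrected)

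None gives 88. Power at 44 per arm is 73.9% by the pooled normal formula and 75.6% by exact enumeration of the Pearson test.

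**Step 5: loss allowance within 120.**

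- Implied by the plan: 120 − 88 = 32, or 26.7%
- From the stated rates: 120 − 105 = 15, or 12.5% (14, or 11.7%, if equal arms of 53 are required)

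The rounding uses 105 − 88 = 17 of the 32.

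**Step 6: if an exact test is used for the stone-free rate.** With equal arms, Fisher's test and the exact chi-square test coincide. Exact enumeration gives:

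- 44 per arm: 67.1%
- 57 per arm: 79.7%
- 58 per arm (116 in total): 80.7%
- 60 per arm (120 in total): 81.5%

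The allowance is then 120 − 116 = 4 patients, about 3%.

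**The case against.** The strongest reply is that the trial enrols 120, not 88. At 120 evaluable the stated rates give 85.3% power by the plan's method and 81.5% even with Fisher's test, so the design meets its target unless more than 12.5% are lost, and the plan gives no loss rate suggesting that they will be. This stands as far as the enrolment figure goes, and it is why no extra patients are asked for. It does not rescue the 88: the plan assigns the surplus to non-evaluable patients, and more than half of it is already spent on the rounding. The 32-patient allowance is a subtraction from the plan's figures, not a loss rate it states, but it is the only reading those figures allow.

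A second reply is that the Thulium rate is only approximate. At 82% the same method gives w = 0.298 and 79.9% power at 88. That shows how sensitive the result is, but the sentence that sets w uses 80% without qualification, and the plan cannot claim 80% power under rates that do not give it.

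Third, 105 is method-dependent. The pooled formula gives 102, exact enumeration of the Pearson test also first reaches 80% at 51 per arm (102 in total), and equal arms require an even number. This is fair: a range of about 102 to 106, with 73% to 76% power at 88, describes the chi-square case. The figure 105 is the like-for-like replacement because it comes from the method that produced 88.

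Finally, the Power analysis section names the chi-square test for this endpoint, and a specific statement normally governs a general one. The Fisher figures are therefore conditional. The two sections still need to agree.

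**Conclusion.** The concern holds. Under the plan's own rates, alpha and method, the effect size is 0.275 rather than 0.3, 88 evaluable patients have about 73% power rather than 80%, and 105 are required. The shortfall at 88 is about 7 percentage points, and the tolerable loss from 120 falls from 26.7% to 12.5%. Planned enrolment remains adequate for the chi-square test if at least 105 patients are evaluable. With Fisher's or the exact chi-square test the requirement is 116 and the margin is close to nil.

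These results assume 1:1 allocation, a two-sided 5% level and true rates of 54.2% and 80%.

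**What to change.** In the Power analysis section:

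- Replace the effect size of 0.3 by 0.275. Calculate from the two rates or the unrounded 0.2746; entering 0.275 itself returns 104.
- Replace the required evaluable total of 88 by 105 (106 if equal arms are to be kept exactly).
- Keep enrolment at 120, and state that it allows for 15 non-evaluable patients (12.5%) and that power at 88 would be about 73%.

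In the Statistical analyses section, name one test for the stone-free rate and make it agree with the power calculation. If that test is Fisher's or the exact chi-square, give the requirement as 116 evaluable patients and say that 120 leaves room for only about 4 losses.

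The cost is wording. No patients are added; the stated margin becomes less favourable.
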